1 SYNOPSIS OF THE STUDY PROTOCOL

1.1 Aim

To study the efficacy of a nurse-led disease management program in community-dwelling patients with moderate-to-severe chronic heart failure (HF).

1.2 Study Design

Open randomized controlled trial, with a parallel-group design and an active control arm.

1.3 Eligibility

- Adult men and women (age: >18 years) with HF who are ensured by Maccabi Health Services in Israel, recruited either <2 months after hospital admission for acute presentation of the disease, or from the community
- Disease severity, assessed by New York Heart Association (NYHA) functional stage:
 - II-IV for patients recruited after hospital admission
 - III-IV for patients recruited from the community
- Heart failure diagnosed according to European Society of Cardiology (ESC) guidelines

1.4 Exclusion Criteria

- Other severe co-morbidity (e.g. end-stage renal failure, severe chronic obstructive pulmonary disease, metastatic cancer)
- Substance abuse (alcohol, illegal drugs)
- People who lack a permanent address or telephone line
- People with significant cognitive impairment / mental disease
- People with severely impaired functional capacity unrelated to heart failure (e.g. bedridden, paraplegic)
- People who are enrolled in another clinical trial
- People who are unwilling to provide a written informed consent

1.5 Randomization

Conducted within 10-patients' blocks and stratified by heart failure center, with 1:1 ratio between the two study arms, maintaining allocation concealment.

1.6 Intervention

1.6.1 Disease Management Study Arm:

- a. Patients assigned to this study arm are managed by a multidisciplinary team at designated heart failure centers (n=9) dispersed countrywide. The team includes nurse specialists, cardiologists, social workers and dietitians. The frequency of follow-up visits will be determined according to clinical needs, but no less than once every 6 months.

- b. Between visits to the heart failure centers, patients were assigned to a nurse disease manager working at a call center, who was in regular contact with the patients, using either telephone calls or computer video-contacts. These sessions were used to receive updated information on patient's signs and symptoms, to modify medical treatment using designated protocols, to promote patient's lifestyle and medication adherence, to coordinate patient's care, and to provide help in case of acute symptoms.
- c. Patients were provided with home tele-monitoring equipment for home blood pressure, heart rate and weight monitoring. The patients' data were automatically entered into the electronic patient record and alerts were produced in case of outlier parameters.

1.6.2 Usual Care Study Arm

Patients assigned to this study arm continued follow-up provided by their family physician and consultant cardiologist. This is the type of care provided to community-dwelling patients with HF by Maccabi Health Services.

1.7 Primary Outcome

First hospital admission for acute exacerbation of heart failure, or death from any cause

1.8 Secondary Outcomes

- I. Total number of hospital days and total number of hospital admissions due to HF
- II. All-cause mortality
- III. Total number of all hospital days and total number of all hospital admissions (for any cause)
- IV. Functional capacity, assessed by:
 - a. 6-minute walk-test
 - b. NYHA stage
- V. Health-related quality of life (using the SF-36 questionnaire)
- VI. Depression symptomatology (assessed by the PHQ-9 questionnaire)
- VII. Change in BNP levels (in a subset of patients)
- VIII. Adherence to medical therapy recommended by ESC clinical guideline for patients with chronic heart failure

1.9 Baseline Assessment and Follow-up Visits at the Heart Failure Centers

Baseline evaluation includes a cardiologist-completed questionnaire on eligibility criteria, medical conditions underlying heart disease; cardiovascular risk factors; and other clinical information related to the patients' heart failure (e.g. presence of arrhythmia, implanted pacemaker or ICD).

- I. Nurse-completed questionnaire on chronic medical therapy.

- II. Nurse-supervised 6-minute walk test.
- III. PHQ-9 and SF-36 questionnaires completed by the patient.
- IV. BNP on-site assessment (starting from 2009).

1.10 Assessment during Follow-up Visits (every 6 months)

Assessment during follow-up visits included all of the baseline evaluation components described above, except for the physician's questionnaire.

Baseline and follow-up assessment visits were conducted for all randomized patients.

1.11 Study Dates

First patient recruited: August, 2007

Last patient recruited: June, 2011

Total number of patients randomized: 1,361 (one not included in the analysis because informed consent was not provided (protocol violation))

Minimum duration of follow-up: 1 year

Maximal follow-up period: 5 years.

2 HANDLING OF MISSING DATA

Missing covariate data will be handled as far as possible by the method of multiple imputation (Little and Rubin, 2002).

3 SUBJECT WITHDRAWALS DUE TO EARLY TERMINATION

Subjects will be censored at the time of last available information, if the endpoint of interest or any competing risk endpoints have not yet occurred.

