Comparison between the two interventions (i.e. Disease Management, the study intervention, and Usual Care, the control intervention) will be made by log-rank test, where an event is defined as hospital admission due to heart failure or death from any cause. In this analysis, the occurrence of any of these two events is defined as 'failure', and the time until the first event (hospital admission or death) will be defined as the time-to-failure. The analysis will be according to intention-to-treat, meaning that patients' data will be analysed according to their assigned intervention. The log-rank test will be one-sided at a significance level of 2.5%, where the alternative hypothesis is that this time will be longer in the study intervention group. Since the Data Monitoring Committee acts as a safety committee and the tests used for this purpose will be in the other direction, looking for poorer results in the study intervention group, no correction for multiple comparisons are needed.

Secondary analyses

There will be several secondary analyses to support the primary hypothesis. They will include:

- (i) Comparisons of baseline factors among the two study groups, e.g. age, NYHA functional classification, 6-min. walk test, left ventricular ejection fraction, type of heart failure, plasma creatinine and heart failure center;
- (ii) Adjustment for these baseline factors will be made using the Cox proportional hazards model;
- (iii) An interaction between the NYHA functional classification and study group will be tested;
- (iv) An interaction between the time of recruitment and study group will be tested, since we expect a 'learning effect' in operating the study intervention;

In addition, the two study groups will be compared for the other secondary outcomes, for example:

- (i) The number of hospital admissions for heart failure per year;
- (ii) Death from all causes;
- (iii) NYHA classification tested every 6 months during follow-up;
- (iv) Health related quality of life and depression symptoms tested every 6 months during follow-up;

Total costs will be compared between the two interventions.

The statistical methods for these comparisons will be chosen according to the distribution of each outcome (categorical, ordered or continuous). Each outcome will be tested in univariate and multiple variable models.

Potential bias and ways to reduce its effect

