4 CLINICAL ENDPOINTS

4.1 Primary Efficacy Endpoint

The primary endpoint of this study is the combined outcome (mortality from any reason or first hospitalization due to heart failure, whichever happens first).

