4.2 Secondary Efficacy Endpoints (events are counted until 31/7/12, ignoring early termination)

The arms will be compared with regard to:

1. Mortality from any reason
2. Hospitalization due to HF
3. Total days of hospitalization and total number of hospital admissions due to HF
4. Total days of hospitalization and total number of hospital admissions due to acute exacerbation of HF
5. Total days of hospitalization and total number of hospital admissions due to HF complications(including HF treatment adverse effects)
6. Total days of hospitalization and number of hospital admissions for any cause
7. Functional impairment (NYHA class) at 6 month intervals until the end of follow-up or end of trial
8. 6-minute walk test at 6 month intervals until the end of follow-up or end of trial
9. Quality of life (SF36 and VAS) at 6 month intervals until the end of follow-up or end of trial
10. Depression (PhQ9) adjusted for baseline value (subgroup with baseline value) at 6 month intervals until the end of follow-up or end of trial
11. BNP since 2009 adjusted for baseline value (subgroup with baseline value) at 6 month intervals until the end of follow-up or end of trial
12. Adherence to guidelines for recommended medical treatment

13. Total cost for health care provider to all health care services supplied to the disease management program (not including cost of disease management manpower and infrastructure designated for the study disease program)
14. Total cost of disease management at 6 month intervals until the end of follow-up or end of trial

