6 DATA ANALYSIS SETS AND BASELINE AND FOLLOW-UP VARIABLES

All analyses will be conducted on the Intention to Treat (ITT) dataset according to the treatment group allocated by randomization. This means that all subjects will be kept in their assigned treatment groups, even those who were intended to be in the active group, but for some reason did not receive the experimental disease management program and vice versa.

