7 EFFICACY ANALYSIS

7.1 Primary analysis of primary endpoint

The analyses to be conducted at the final statistical analysis are described in this Section. The primary endpoint is time to the combined outcome (mortality or hospitalization due to heart failure, whichever happens first). The Cox regression model will be used to compare the treatment groups with respect to this outcome, and the comparison will be adjusted for the following baseline factors: sex, age (5 categories: <50, 50-59, 60-69, 70-79, 80+), center, and functional impairment (NYHA class) at baseline.

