7.2 Secondary analyses

7.2.1 Secondary Analyses of the Primary Endpoint

All analyses will be adjusted for the same baseline factors as mentioned in 7.1 plus others that are unbalanced between the treatment groups, i.e are significantly different at the 10% significance level when entered separately. The additional baseline factors that will be considered are:

- A. 6-minute walk test
 - B. Recruited after hospitalization or from the community
 - C. Year of recruitment
 - D. Underlying cause of heart failure: ischemic/non-ischemic
 - E. Type of heart failure (left ventricular ejection fraction (LVEF) %): preserved (LVEF (%) \geq 50%)/ non-preserved (LVEF%)<50%.
 - F. Co-morbidity: diabetic/ non-diabetic
 - G. Adherence to HF medication
1. The principal statistical analysis mentioned in 7.1 with additional adjustment.
 2. Cox regression for the outcome mortality from any cause.
 3. Cox regression with the outcome re-hospitalization due to heart failure.

For each of these outcome models, the following interactions will be tested:

- i. Between arm and year of recruitment
- ii. Between arm and center
- iii. Between arm and recruitment after hospitalization or from the community
- iv. Between arm and underlying cause of HF (ischemic/ non-ischemic)
- v. Between arm and type of HF (preserved (LVEF \geq 50%)/ non-preserved (LVEF<50%))
- vi. Between arm and co-morbidity (diabetic/ non-diabetic)
- vii. For outcomes (1)-(3) above, we will investigate the interaction between treatment arm and time from entry to the trial. This is equivalent to testing the assumption

that the hazards in the two treatment arms are proportional over time – what is known as the proportional hazard assumption.

7.2.2 Analyses of Secondary Endpoints (events are counted until 31/7/12, ignoring early termination)

Fourteen secondary end-points will be analyzed to provide insight into the benefits of the disease management program. The analyses will be conducted on the ITT dataset. All the analyses will be adjusted for the following baseline factors:

- A. Sex
- B. Age (in five groups, as above)
- C. Center
- D. Functional impairment (NYHA) at baseline

- 1. Cox regression with mortality due to any cause.
- 2. Cox regression with re- hospitalization due to HF
- 3. Regression with total days of hospitalization and total number of hospital admissions due to HF
- 4. Regression with total days of hospitalization and total number of hospital admissions due to acute exacerbation

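### The SAP fixes a follow-up window that ignores early termination for the secondary endpoints only, so deaths and HF admissions counted there can be left out of the primary composite

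*Supplement*

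**What the plan says.** - SAP 3, the rule for patients who stop early: "Subjects will be censored at the time of last available information". This applies provided that neither the event under analysis nor a competing one has happened by then. The rule is not tied to any one endpoint, and neither early termination nor last available information is defined.
- SAP 4.1: "The primary endpoint of this study is the combined outcome (mortality from any reason or first hospitalization due to heart failure, whichever happens first". No counting window is given.
- SAP 7.1: "The Cox regression model will be used to compare the treatment groups with respect to this outcome", with adjustment for sex, age, center and NYHA class. No censoring date is given.
- SAP 4.2, heading: "Secondary Efficacy Endpoints (events are counted until 31/7/12, ignoring early termination". Items 1 and 2 of that list are all-cause mortality and HF hospitalization, the two components of the primary composite.
- SAP 7.2.2, heading: "Analyses of Secondary Endpoints (events are counted until 31/7/12, ignoring early termination".
- SAP 7.2.1, items 2 and 3: further Cox models for mortality and HF re-hospitalization, without the 31/7/12 wording.
- SAP 6: "All analyses will be conducted on the Intention to Treat (ITT) dataset according to the treatment group allocated by randomization". The protocol's main analysis likewise specifies intention to treat by assigned intervention.

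**The concern.** The SAP's authors wrote the words that set early termination aside twice, each time for secondary endpoints. If section 3 already carried every patient to 31/7/12, those words would add nothing. The natural inference is that two follow-up rules are in play and that the primary composite falls under the shorter one.

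That matters for three reasons. First, a patient who terminates early in 2009 and dies in 2010 would be a death in secondary endpoint 1, yet could be a censored observation in the primary. Second, the trial is open-label and only one arm has nurse calls and tele-monitoring to abandon, so withdrawal related to both prognosis and arm cannot be ruled out. Third, if last available information means last contact, the censoring date itself may depend on arm. Under the protocol, planned nurse calls in the intervention arm update information on recent admissions between visits, whereas control patients see the heart failure centre every 6 months. With the rule left open, two competent analysts could produce different primary hazard ratios from the same data.

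**Working it through.** **1. The rules side by side**

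| Analysis | SAP place | Follow-up rule stated there |
|---|---|---|
| Primary composite | 4.1, 7.1 | None; section 3 applies by default |
| Composite, extra adjustment | 7.2.1 item 1 | None |
| Mortality; HF re-hospitalization, extra adjustment | 7.2.1 items 2-3 | None |
| Mortality; HF hospitalization | 4.2 items 1-2, 7.2.2 items 1-2 | To 31/7/12, early termination ignored |

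The same events therefore have a fixed window as secondary endpoints and an undefined one inside the primary.

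**2. The plan's nearest figure**

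The censoring rule has no figure to reproduce. The closest is the protocol's power for 12-month re-hospitalization, its proxy for the composite: 600 per arm, control rate 33%, odds ratio 0.67, two-sided 5%, stated power 89%.

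- Control odds 0.33/0.67 = 0.4925; times 0.67 = 0.330; experimental rate 0.330/1.330 = 0.248.
- Difference 0.0819; SE under the null (pooled rate 0.289) 0.02617; SE under the alternative 0.02607.
- z = (0.0819 − 1.96 × 0.02617)/0.02607 = 1.17, so power is 88.0%. This agrees with the stated 89% to within about a point.

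**3. Power if events are lost (the fraction lost is assumed)**

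Power = Φ(√D × |ln HR|/2 − 1.96), with 1:1 allocation and D events.

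- Scenario A: D = 680 × (0.33 + 0.248) = 393, from 1,360 patients at the protocol's 12-month rates. HR = ln(1 − 0.248)/ln(1 − 0.33) = 0.71.
- Scenario B: D = 600 and HR = 0.80, both assumed.

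| Events lost | A | B |
|---|---|---|
| 0% | 92.0% | 78.0% |
| 5% | 90.7% | 75.9% |
| 10% | 89.1% | 73.7% |
| 20% | 85.3% | 68.6% |

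**4. Bias if patients are censored at withdrawal (all inputs assumed)**

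*With a treatment effect.* Simulation of 20,000 per arm, control hazard 0.40 per year, individual risk multiplier f (gamma, mean 1, variance 0.5), conditional HR 0.80, follow-up uniform over 1 to 5 years. The full-follow-up HR is near 0.83 rather than 0.80 because of f. It varies between runs by sampling error (SE of ln HR about 2/√22,000 = 0.013), so only the change within a row should be read.

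| Withdrawal rate per year, control / intervention | HR, full follow-up | HR, censored |
|---|---|---|
| 5% / 5%, unrelated to risk | 0.833 | 0.835 |
| 5% / 5%, proportional to f | 0.828 | 0.826 |
| 2% / 8%, proportional to f | 0.830 | 0.807 |
| 8% / 2%, proportional to f | 0.831 | 0.854 |
| 2% / 8%, proportional to f² | 0.849 | 0.802 |

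The first four rows lose about 6% of events and the last about 9%.

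*With no treatment effect.* 1,360 patients, hazard rising from 0.30 to 1.0 per year at deterioration (deterioration rate 0.3 per year), some patients withdrawing at that moment.

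- About 12% withdrawn on intervention and 4% on control: HR about 0.95, type I error about 12% to 14% over repeated runs.
- About 12% and 0%: HR 0.92 to 0.93, type I error about 19% to 23%.
- About 8% in each arm: no bias, but about 84 of 957 events (9%) lost.

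Bias therefore needs withdrawal that is both informative and different between arms. Its sign follows whichever arm loses more high-risk patients.

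**The case against.** The strongest reply is that no sentence in the SAP censors the primary at the date of withdrawal. Section 3 refers to last available information and applies only if the endpoint has not yet occurred. If vital status and admissions are known to 31/7/12, that date can literally be the last available information, and a known 2010 death is then an event. Section 3 is also not confined to the primary: its mention of competing risks fits HF hospitalization better than a composite that already contains death. The counting words in 4.2 may have been written for the totals of days and admissions, which need an explicit window. The Summary of Changes describes retrieval of missing discharge summaries and completed adjudication after the study ended, which points towards full ascertainment.

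Most of this stands, and it rules out stronger statements that a reader might infer:

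- *That the plan certainly drops known events.* The text permits this reading and makes it the natural one, but does not state it.
- *That the primary analysis is not ITT.* Section 6 keeps every patient in the allocated arm. It settles who is analysed and in which group, but not for how long they are followed.
- *That the two mortality models prove two censoring rules.* The 7.2.1 models may also carry extra covariates, those unbalanced at the 10% level, so two estimates could arise with identical follow-up.
- *That the result is biased towards the intervention.* The documents give no count, timing or reasons for early termination.

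The reply does not supply a fixed censoring date for the primary. It works only if an undefined term is read in one particular way.

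**Conclusion.** The point holds as an unresolved follow-up rule for the primary endpoint. On the natural reading, post-termination deaths and HF admissions that the SAP counts as secondary events can be absent from the primary composite. On the alternative reading they are included, but the SAP does not say so.

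The certain consequence is ambiguity in the primary analysis. The possible consequences are lost events and a biased hazard ratio of unknown direction. Their size cannot be derived from the documents. In the assumed scenarios, losing 5% to 20% of events costs about 1 to 9 points of power (92.0 − 90.7 = 1.3; 78.0 − 68.6 = 9.4), and differential, risk-dependent withdrawal moves the hazard ratio by about 0.02 to 0.08. These figures assume censoring at withdrawal, the very point the SAP leaves open, and are illustrative only. Withdrawal at equal rates in the two arms produced essentially no bias.

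It merits correction because it concerns the primary endpoint, and the SAP already contains the rule needed.

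**What to change.** 1. In SAP 4.1 and 7.1, state that primary events are counted to 31/7/12 regardless of early termination, with earlier censoring only where death and admission records are truly unavailable. Item 1 of 7.2.1 then inherits the rule.
2. Apply the same statement to 7.2.1 items 2 and 3, so that they differ from 7.2.2 items 1 and 2 only in covariates.
3. In section 3, define early termination (for example, leaving the programme as distinct from withdrawing from follow-up) and last available information. Tie the latter to record availability, not to the last nurse call or clinic visit.
4. Keep censoring at early termination as a labelled sensitivity analysis, and report early terminations and subsequent events by arm.

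The cost is SAP wording and one extra model run. The SAP already plans to use these events for the secondary endpoints, so no new data collection is needed.

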4 CLINICAL ENDPOINTS

4.1 Primary Efficacy Endpoint

The primary endpoint of this study is the combined outcome (mortality from any reason or first hospitalization due to heart failure, whichever happens first).

4.2 Secondary Efficacy Endpoints (events are counted until 31/7/12, ignoring early termination)

The arms will be compared with regard to:

1. Mortality from any reason
2. Hospitalization due to HF
3. Total days of hospitalization and total number of hospital admissions due to HF
4. Total days of hospitalization and total number of hospital admissions due to acute exacerbation of HF
5. Total days of hospitalization and total number of hospital admissions due to HF complications(including HF treatment adverse effects)
6. Total days of hospitalization and number of hospital admissions for any cause
7. Functional impairment (NYHA class) at 6 month intervals until the end of follow-up or end of trial
8. 6-minute walk test at 6 month intervals until the end of follow-up or end of trial
9. Quality of life (SF36 and VAS) at 6 month intervals until the end of follow-up or end of trial
10. Depression (PhQ9) adjusted for baseline value (subgroup with baseline value) at 6 month intervals until the end of follow-up or end of trial
11. BNP since 2009 adjusted for baseline value (subgroup with baseline value) at 6 month intervals until the end of follow-up or end of trial
12. Adherence to guidelines for recommended medical treatment

13. Total cost for health care provider to all health care services supplied to the disease management program (not including cost of disease management manpower and infrastructure designated for the study disease program)
14. Total cost of disease management at 6 month intervals until the end of follow-up or end of trial

